Device(s) being tested:	Device under evaluation: Navii (also known as Rheo Knee 4), a pre-market passive exo-prosthetic microprocessor controlled knee device. Comparator: Subjects prescribed passive microprocessor knee, marketed device. For simplification the device under evaluation in this investigation will be referred to as “investigational device” throughout this document.	
Instruments and equipment:	Instruments: 
 • SFCS Socket fit comfort score • PEQ ambulation subscale (Questions 13A, 13B, 13C, 13D, 14E, 14F, 14G, 14H) • PEQ Utility questions (Questions 2G, 2F) • PEQ Satisfaction Questions (Questions 16A, 16B) • Device and performance specific questionnaires • TUG, 2MWT, ABC, PLUS-M. Equipment: 
 • Investigational device (see section 5 Investigational device) • Other components as applicable (prosthetic feet, adapters) • Tools for fitting • Detailed protocol • Case report forms (CRFs); in Smart-Trial – Tablet/computer OR Printed out Case report forms (CRFs including instruments listed above) 	
Subjects recruited:	Inclusion criteria:	Exclusion criteria:
Procedures:	
 - 45Kg < body weight < 136Kg - Cognitive ability to understand all instructions and questionnaires in the study; - Unilateral TF/KD amputees that are regular prosthesis users for at least 3 months - Current MPK users (passive MPKs only) regularly performing descent activities (stairs/ramps) - Age ≥ 18 years - Willing and able to participate in the study and follow the protocol 	
 - Users with stump pain - Users with socket problems - Pregnant Users - Users using Power Knee, Kenevo or mechanical knees as their prescribed prosthesis - Alignment that cannot be matched with the Navii setup, as described in Instructions for use. - Osseointegration

	
consent.
 
Prior to fitting the subject will be asked to provide feedback on the current prosthesis, by filling in a set of questionnaires (including subset of PEQ) and perform tasks of daily living like e.g., walking up/down ramps and stairs, level ground walking in different speeds and walking on uneven terrain.
 
The users will be fitted within the standard methods of prosthetic fitting and alignment will be documented.
 
After initial fitting of the investigational device, the subjects will receive standard training on the investigational device. The required training steps and exercises as well as the performance of the subject will be observed. Comments and initial feedback from the subject will be documented. When the training is completed, and subjects feel comfortable and safe they will take a short break. Afterwards they will be asked to perform the same tasks as with their prescribed prosthesis before.
 
A standardized set of questions regarding the performance of the investigational device and the subject's satisfaction will be asked as a semi-structured interview, and the responses are documented. After the first feedback round with the investigational device, different modes for descent activities may be tested. The investigator may change the modes and settings. The changes might be subtle; subjects will be asked if they feel a difference. Eventually the subjects shall evaluate if they prefer a mode.
 
The activities are video recorded to visually compare the performance of the two devices.
 
If the user feels comfortable and safe, he will be asked to use the investigational device for 4 weeks. They will be asked to fill in a log file for e.g. use in water, use of the app, use of the locking function.
 
The LPI will contact the user after 2 weeks to check on any issues that may arise. The user has the option to stop the trial at any time, an appointment will be made to switch to the prescribed knee.
 
The second visit will be at 4 weeks after visit 1. During this visit subjects will complete the same functional tests and questionnaires as at visit 1 (excluding background information) on the investigational device. They will then be fitted back to their prescribed device.
 
See Table 1 below.

Objective	
In this trial, the primary objective is to evaluate the efficacy of the investigational device compared to the former Version Rheo Knee (XC) and in addition (mandatory) to other passive MPKs (e.g. C-leg 4, Genium, X3, Plié 3, Orion 3, Quattro, Allux) regarding performance improvements and satisfaction in descending activities for moderate to high active prosthesis users within the intended population for the investigational device.
 
Additionally, the overall satisfaction for activities of daily living will be evaluated after a certain time of use (4 weeks home use).

Table 1 Summary of procedures and visits

	Recruitment phase: 2-4 weeks prior to baseline	Subject visit 1: baseline	Subject visit 2: 4 weeks after visit 1
Potential subjects identified, fitting inclusion/exclusion criteria, by LPI from Össur customers	X		
LPI calls potential subjects and screens by telephone	X		
Subject signs ICF		X	
Subject performs activities of daily living (Ramps, stairs, uneven terrain)		X	
Subject fills in set of questionnaires		X	
Subject fitted with investigational device and receives training according to training protocol			X
Subject performs activities of daily living (Ramps, stairs, uneven terrain)			X
Subject fills in set of questionnaires			X
LPI prints out activity report from the investigational device/ prescribed device			X
Subject is fitted back to their prescribed prosthesis			X
End of study			X

3 Changes from Previous Revision

3.1 Changes for Revision 1.00

Initial release December 2023.

4 Abbreviations

ADE	Adverse Device Effect
AE	Adverse Event
AR	Adverse Reaction
BL	Baseline
CA	Competent Authority
CEP	Clinical Evaluation Plan
CER	Clinical Evaluation Report
CI	Co-Investigator
COI	Coordinating Investigator
CIB	Clinical Investigator's Brochure
CIP	Clinical Investigation Plan
CIR	Clinical Investigation Report
CRF	Case Report Form

CRO	Clinical Research Organisation
CT	Clinical Trial
CTA	Clinical Trial Authorisation
EC	Ethics Committee (see IEC, IRB, REB and REC)
EDS	Electronic Data capture Service
FU	Follow-Up
GCP	Good Clinical Practice
CIB	(Clinical) Investigator Brochure
ICF	Informed Consent Form
IDMF	Investigational Device Management Form
IEC	Independent Ethics Committee
IFU	Instructions For Use
IRB	Independent/Institutional Review Board
LCI	Local Co-Investigator
LPI	Local Principal Investigator
LRA	Local Research Assistant
PI	Principle Investigator
PIS	Participant Information Sheet
REB	Research Ethics Board
REC	Research Ethics Committee
SAE	Serious Adverse Event
SADE	Serious Adverse Device Event
SOP	Standard Operating Procedure
SOTA	State-Of-The-Art
SRA	Sponsor Research Assistant
USADE	Unanticipated Serious Adverse Device Effect

5 Investigational Device

The investigational device is a pre-market device and will be labeled according to regulations concerning pre-marketed investigational devices.

See Table 2 for details on the investigational device.

Table 2 Identification and Description of the Investigational Device

Summary description of the investigational device and its intended purpose:	
The investigational device, Rheo Knee 4 which will be marketed under the name NAVii, is a passive microprocessor-controlled prosthetic knee. It is a Class II product and is a further development of a well-established technology.
 
The device is classified as an “External assembled lower limb prosthesis” according to Title 21 §890.3500, bearing the product code ISW (Assembly, Knee/Shank/Ankle/Foot, External)
 
It is 510(k) exempt, except for general requirements.
 
It is composed of a microprocessor-controlled prosthetic knee, a power supply and a configuration software. Sensors within the prosthetic knee prosthesis provide continuous real-time information. This data is utilized to control the braking torque of the joint via activating a magnetorheological actuator. Via the configuration software, running on an external computing device, a wireless link to the prosthetic knee prosthesis can be established. Through this the investigational device can be optimized with respect to the end users’ gait, physical characteristics and personal

---	--

	
preferences.
 
The investigational device supports prosthetic use from simple locomotion to ambulation with variable cadence and traverse of various terrains. Additionally, it offers features as step-over-step stairs and ramp walking, running, and cycling.
 
Exo-prosthetic devices are by their nature non-invasive. The investigational device is a non-sterile, reusable (i.e. non-disposable), single user device, which is used as part of prosthetic system.
 
The Investigational device is a programmable electrical medical system (PEMS). Its essential performance is defined as structural support, as loss of structural support does not allow the device to fulfill its intended use. Loss of the PEMS related operation on the other hand allows the user to continue walking even if the performance and feature set provided by the device are reduced.
 
The Investigational device is an internally powered device when operated in its intended medical purpose.
 
Device Intended purpose:
 
The Investigational device is intended as part of a prosthetic system that replaces knee function of a missing lower limb.

Manufacturer of the investigational device:	Össur hf. [name]
Name or number of the model/type, including software version and accessories, if any, to permit full identification:	Model: NAVII [REDACTED]
Traceability during and after the investigation:	Investigation Device Management Form (IDMF) will be used to track the use of each device within the clinical investigation using the device serial number.
Intended purpose of the investigational device in the proposed clinical investigation:	
Intended purpose of the investigational device in the proposed clinical investigation is within the intended purpose as described above.
 
See following chapters on the intended purpose of the investigational device in the proposed clinical investigation for details.

The populations and indications for which the investigational device is intended:	
Intended Purpose Statement
 
The device is intended as a part of a prosthetic system that replaces knee function of a missing lower limb.
 
Indications for Use(s)
 
Lower limb loss, amputation or deficiency.
 
Contraindications for Use(s)
 
No contraindications for use are known for Navii / Rheo Knee 4.
 
Intended Patient Population
 
Medical conditions: Transfemoral / knee disarticulation amputation;
 
Activity Level: Moderate to high-active ambulators
 
 - Community ambulators;

	
Impact Level: - Ambulation exceeding basic ambulation needs or skills. User Weight: Low to high impact levels. Higher than 45kg; Lower than 136kg (110kg for high impact use).


Description of the investigational device:
	
See Table 3 below for descriptions of device features and their relation to the investigation.
  
Figure 1 Investigational device as final product
 
The investigational device is composed of a microprocessor-controlled prosthetic knee, a power supply and a configuration software. Sensors within the prosthetic knee provide continuous real-time information. This data is utilized to control the braking torque of the joint via activating a magnetorheological actuator. Via the configuration software, running on an external computing device, a wireless link to the prosthetic knee prosthesis can be established. Through this the investigational device can be optimized with respect to the end users' gait, physical characteristics and personal preferences.
 
The aspect of the prosthesis that is in direct physical contact with the amputee is usually a liner that serves as an interface between the amputee and the rest of the prosthesis. In other words, the device is usually not in direct physical contact with the amputee.
 
As described above, the device is intended to be in contact with intact skin only.
 
The device does not incorporate, as an integral part, a substance or human blood derivative and is manufactured without utilizing tissues of animal origin.

Summary of the necessary training and experience needed to use the investigational device:
	
Training requirements for subjects and procedures relating to fitting and use of a device will for all general purposes be equivalent to the training and procedures required for using a FDA approved/CE-marked device of a similar type. The device should be supplied and fitted by a certified CPO/CO/CP.

	For the purpose of this investigation training for subjects will be standardized to assure that all subjects will receive the same training.
Specific medical or surgical procedures involved in the use of the investigational device:	N/A

6 Justification for the Design of the Clinical Investigation

The term microprocessor-controlled (MPC) refers to components that are intelligently regulated in real time by one or more onboard microprocessors that modify some characteristic of their behavior according to either environmental or user inputs.¹ MPC prosthetic knees, often referred to as MPKs, are battery-powered and use algorithms based on input received from load sensors, accelerometers, gyroscopes, and joint angles to initiate the transition from stance to swing phase ²⁻⁶. MPC prosthesis have been shown to offer clinical advantages compared with mechanically controlled alternatives,⁷ and appears to be the direction of development in contemporary prosthetic research and development.⁸

The main advantage is an increased ability to allow safe ambulation ^{2,4,5,9-11}, reduced cognitive dedication to controlling the knee unit,^{2,12} reduced force required to initiate knee flexion,¹⁰ increased gait efficiency,^{2,4} and increased overall user confidence with the prosthesis ^{2,5}. The MPC knee increases comfort and improves walking speed in active users. ^{4,6,13,14} The main disadvantage has been the intolerance of dust or moisture, and its increased requirement for maintenance and repair.¹⁵

Microprocessor Controlled Knees (MPK) have become the standard of care for trans-femoral amputees of medium to high activity levels (K3-K4). While the functional principles of the different knee joints remain the same, differences in the mechanical design can be found.

The investigational device is a microprocessor-controlled prosthetic knee and employs sensory information, to automatically adapt knee damping values to match the amputee's gait requirements, accounting for variations in forward walking speed, walking terrain, user gait styles and body size. The investigational device technology generates resistances with a microprocessor-controlled, magnetorheological fluid, which enables continuous variation of knee joint resistances in both movement directions. The amount of current determines the viscosity of the fluid. Therefore, an adaptable friction moment is generated for both flexion and extension movements at the same time. In this study there are two types of comparator devices, hydraulic MPKs and previous version of the investigational device.

Hydraulic MPKs consist of an integrated microprocessor-controlled linear hydraulic system in combination with a control algorithm. They generate knee joint resistances hydraulically with microprocessor-controlled, motorized valves. This enables continuous variations in the hydraulic resistance to be set for both movement directions. The magnetorheological fluid creates shear forces in comparison to an increase of pressure in a hydraulic system. The increased system pressure can lead to higher temperatures and risk of leakage.

The previous version of the investigational device (RK III/RK XC) features the same intended use, same clinical purpose, same user population, same placement below the socket, uses a battery powered system and is controlled through a software application that can be user configured through a separate computer interface/mobile device. The investigational device is an enhancement of the previous version, functional features and indication are equivalent to previous version and the same critical functions apply. Features that have been added include a mechanical stance locking feature that allows the user to manually lock the knee in 3 different positions in stance and the device will be waterproof. The investigational device also includes functions that were only included in the Rheo Knee XC configuration of the previous version; automatic cycling and running detection and a stair ascent mode.

Results of a pilot stage exploratory clinical investigation including 25 subjects indicate that the investigational device had similar or better performance compared to previous versions of the Rheo knee regarding satisfaction on descending activities. This investigation is designed primarily to confirm these indications and that the performance of the investigational device regarding descending activities is comparable/no worse than Rheo Knee or hydraulic MPKs.

Study Design

[figure not shown]

Figure 2 - Study design and instruments

Repeated measures analysis has the advantage of increased power compared to group allocations and reduction in error variance associated with individual difference, as each subject acts as its own control. This is important for studying amputees as the group is a small proportion of the total population, and with specific inclusion/exclusion criteria the total eligible population becomes very small, making it difficult to find and recruit subjects to attain an acceptable level of power. This limited population pool often results in a slightly heterogeneous sample, as the amputees available are few and far between, in every sense. Furthermore, no single amputation procedure and therefore amputated stump is exactly the same, making the experience of each amputee unique. The within-subject design significantly reduces the individual differences when comparing the two conditions.

Several studies have provided evidence for the clinical performance of previous versions of the Rheo Knee, which is equivalent to the investigational device and has the same function and intended use, those are detailed in the Literature review device report [1]. The current study is due to a design iteration after modifications to the device from the previous study CIP2022022514 [9].

[figure not shown]
For full details of existing clinical data and pre-clinical data on the investigational device see Investigators Brochure [2].

7 Objectives and Hypotheses

In this trial, the primary objective is to evaluate the efficacy of the investigational device compared to the former Version Rheo Knee (XC) and in addition (mandatory) to other passive MPKs (e.g. C-leg 4, Genium, X3, Plié 3, Orion 3, Quattro, Allux) regarding performance improvements and satisfaction in descending activities for moderate to high active prosthesis users within the intended population for the investigational device.

Additionally, the overall satisfaction for activities of daily living will be evaluated after a certain time of use (4 weeks home use).

The following clinical claims/MNBA items as defined in the Clinical evaluation plan [3] are to be evaluated:

The hypothesis and endpoints are specified in Table 4 and Table 5.

For all hypothesis:

[figure not shown]
μ_1 is average of measurements at baseline (comparator);

[figure not shown]
μ_2 is the average of measurements at 4 week follow up (investigational device);

Table 5 - Endpoints, test methods and hypotheses

	Hypothesis	Construct & Test Methods	Endpoints	Acceptance Criteria
A	Navii shows better or no worse results in Ramp, Stairs and Level Ground activities compared to prescribed prosthesis	Specific questions (see Annex 8.8)	Rating: Same, better, worse	Overall results for Navii are same or better than for Rheo Knee, with no more than 20% rating it worse, overall for all questions.
B	Navii shows a good level of overall satisfaction in activities of daily living	Subset of PEQ (see Annex 8.4) Specific Questions (see Annex 8.8)	PEQ Rating	Comparison Subset PEQ pre vs post. Navii not worse than prescribed.
C	Mobility is no worse with Navii compared to prescribed MPK	2 MWT	Distance walked in 2MWT (meters)	No significant reduction in distance walked on 2MWT with prescribed knee/Navii
D	Balance during ambulation is no worse with Navii compared to prescribed MPK	TUG	Time to complete TUG (seconds)	No significant increase in time needed to complete TUG with prescribed knee/Navii
E	Mobility is no worse with Navii compared to prescribed MPK	PlusM	PlusM Score	No significant reduction in PlusM Score with prescribed knee/Navii
F	Gather experiences on perceived safety and balance with Navii compared to prescribed knee.	ABC	ABC Score (0-100%)	Acceptable patient-reported perceived safety and performance

7.1 Additional Outcome measures:

8 Design of the Clinical Investigation

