8.2 Investigational Device(s) and Comparator(s)

The subjects will be asked to use the investigational device as their primary prosthesis for **4 weeks**. Individual exposure will differ between subjects. Subjects are expected to use it for their daily living activities as they would with any other prosthesis, for up to 18 hours a day depending on the amputee. The comparator device will not be used within the timeframe of the investigation. Subjects will evaluate and provide feedback on their exposure of the comparator prior to them being fitted to the investigational device.

The comparator device will be the former version Rheo Knee (XC) or any other passive microprocessor controlled prosthetic knee (excluding Kenevo as it does not have the same intended patient population as the investigational device). They have the same intended use as the investigational device. Furthermore, they are indicated for the same condition and population group. Passive MPKs are widely accepted devices, providing clinical benefits to the user.

Where possible, the subject will be using the remaining part of their current prosthetic system with the investigational device, as it was used with the comparator device. In some cases where a subject is using components from other manufacturers (e.g. feet not validated for use with the investigational device) compatible components will be provided.

No other device, medication or intervention will be used.

Up to 13 subjects are to be enrolled and therefore 13 investigational devices will be used, as the devices are intended to be used by a single patient; one for each subject.

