8.3 Subjects

All subjects will be dispositioned as follows:

- Screen Failure: Subject did not pass screening procedures, not called in for clinical visit;
- Candidate for enrollment: Passed screening procedures, accepts to come in for clinical visit;
- Enrolled: Subject signs informed consent and takes part in the first experimental session;
- Fitted: Subject leaves the clinic on the investigational device;
- Drop-out: Enrolled subject whose participation ended because they did not want to continue participation.
- Discontinued: Candidate for enrollment or Enrolled subject whose participation ended because they withdrew consent, were withdrawn by the Investigator, were lost to follow up, or died.

Table 6 Inclusion/Exclusion criteria

Inclusion:	Exclusion:
Only patients with the following characteristics are eligible for study entry:	Patients with the following characteristics are not eligible for study entry:
45Kg < body weight < 136Kg	Users with stump pain*
Cognitive ability to understand all instructions and questionnaires in the study;	Users with socket problems**
Unilateral TF/KD amputees that are regular prosthesis users for at least 3 months	Pregnant Users***
Current MPK users (passive MPKs only) regularly performing descent activities (stairs/ramps)	Users using Power Knee, Kenevo or mechanical knees as their prescribed prosthesis
Age \geq 18 years	Alignment that cannot be matched with the Navii setup, as described in Instructions for use.
Willing and able to participate in the study and follow the protocol	-Osseointegration

*Question on pain affecting their functional ability (yes/no)

**Socket fit: Socket fit comfort score over 5

*** Self reported

A subject can withdraw from participation at any time, at his/her discretion, and this will not have any consequences for the participant's treatment. In such cases a report stating reasons for discontinuation of the participant shall be prepared by the **LPI**. No further investigational procedures concerning the subject will be conducted, except for a statement explaining the reason for withdrawal, including but not limited to: interacting or interviewing the subject in order to obtain data on him/her; obtaining additional private information on the subject by either observing the subject or collecting or receiving such information from any source.

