A standardized set of questions regarding the performance of the investigational device and the subject's satisfaction will be asked as a semi-structured interview, and the responses are documented.

The activities are video recorded to visually compare the performance of the two devices.

If the user feels comfortable and safe, he will be asked to use the investigational device for 4 weeks. They will be asked to fill in a log file for e.g. use in water, use of the app, use of the locking function.

The LPI will contact the user after 2 weeks to check on any issues that may arise. The user has the option to stop the trial at any time, an appointment will be made to switch to the prescribed knee.

The second visit will be at 4 weeks after visit 1. During this visit subjects will complete the same functional tests and questionnaires as at visit 1 (excluding background information) on the investigational device. They will then be fitted back to their prescribed device and feedback will be collected.

iii) Measurements and data collection

The same questionnaires, consisting of one valid instrument (subset of PEQ questions) and device and performance specific questionnaires, will be used and filled in at two separate points in time. Background information will be collected at baseline only. An activity report will be generated from the investigational device at visit 2.

Table 7 Visit schedule and procedures

	Recruitment phase: 2-4 weeks prior to baseline	Subject visit 1: baseline	Subject visit 2: 4 weeks after visit 1
Potential subjects identified, fitting inclusion/exclusion criteria, by LPI from Össur customers		X	
LPI calls potential subjects and screens by telephone (Pain Scale, SFCS)		X	
Subject signs ICF		X	
Subject answers subset of PEQ		X	
Subject performs TUG, 2MWT and activities of daily living (Ramps, stairs, uneven terrain)		X	
Subject fills in set of questionnaires (ABC, PlusM)		X	
Subject fitted with investigational device and receives training according to training protocol		X	
Subject performs activities of daily living (Ramps, stairs, uneven terrain)		X	
Subject fills in set of questionnaires (Specific questions, comparison)		X	
Subject answers subset of PEQ		X	
Subject performs TUG, 2MWT and activities of daily living (Ramps, stairs, uneven terrain)		X	
Subject fills in set of questionnaires (ABC, PlusM)		X	
LPI prints out activity report from the investigational device/ prescribed device			X

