13.2 Device related risk

[figure not shown]
Each device designed and manufactured by Össur is subjected to thorough risk assessment, analysis and control, with failure mode effect analysis and hazard analysis, according to PR-00032 Risk Management process, based on ISO 14971 [5] (Risk Management for Medical Devices). All changes performed to the software and/or functions of a device are submitted to multi-level verification and, as applicable, validation processes before being authorized for use in a clinical investigation.

The FMEA and hazard analysis are tools for identifying harms, the sequence of events, their probability, and the potential failures that can cause these harms. Anticipated adverse device effects and residual risks associated with the investigational device, are identified in the Hazard Analysis Documentation [4] and Chapter 7 in the Clinical Investigator's Brochure [2].

The design criteria are an important input in the risk analysis but also the experience of existing products of similar function and/or type (Post market surveillance data). The Rheo Knee 3 (incl. XC configuration) is an equivalent device currently marketed by Össur; post-market surveillance reporting provides data on device related risks as experienced in the real-world application of the device:

Post Market Surveillance

Outcome from Post Market Surveillance (PMS) data has not given reason to update risk management documents. No new harm has been identified from the PMS data and results from analysis do not impact conclusion on final risk assessment.

The following reasonably foreseeable misuses have been identified based on current knowledge about transfemoral prosthetic devices and microprocessors-controlled prosthetic knees.

- Use of product by user exceeding the maximum user weight.
- Use of product by user not meeting the minimum user weight.
- Failure to properly maintain the product and/or maintain the product to the expected level of cleanliness.
- Product contamination by foreign substances or operation of the product in dirty or dusty environments.
- Failure to follow recommended or mandatory service schedule.
- Use of the product over the specified maximum life duration.
- User does not read user manual.
- User cannot read user manual.
- User's clinician is insufficiently trained.
- User receives insufficient training from clinician(s).

- Memory failure (user forgets clinicians' training/advice).

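### The 110 kg limit for high impact use in Table 2 is not carried into the eligibility criteria or the visible home-use text

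*Combined protocol and SAP*

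**What the plan says.** Section 5, Table 2 describes the intended patient population. It covers "Low to high impact levels", requires more than 45 kg, and gives the upper weight as "Lower than 136kg (110kg for high impact use").

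The weight criterion in Section 8.3, Table 6, worded the same way in the synopsis, is "45Kg < body weight < 136Kg". Neither list has a criterion on impact level.

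On home use, Section 8.4 says: "If the user feels comfortable and safe, he will be asked to use the investigational device for 4 weeks". Section 8.2 says: "Subjects are expected to use it for their daily living activities as they would with any other prosthesis". Section 13.3 likewise expects the trial device to be used just as the subject uses the current one.

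On what the device can do, Table 2 says: "Additionally, it offers features as step-over-step stairs and ramp walking, running, and cycling". Section 6 adds that it includes "automatic cycling and running detection and a stair ascent mode".

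**The concern.** Table 2 has two upper weights, depending on use, and the operative criteria keep only the higher one. Site staff screen against Table 6, so a condition that appears only in the device description can be missed.

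The home-use text makes the omission matter more. Release home depends on the user feeling comfortable and safe, and the user is then expected to carry on as usual. Someone whose usual use is high impact is in effect told to continue it. Under Section 8.2 the comparator is not used during the study, and under Section 14.2 the prescribed prosthesis stays at the site, so the subject cannot readily go back to it for a particular activity.

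At stake is the safety of a subject who was enrolled correctly under Table 6 but is using a pre-market device outside its stated population. Table 2 defines the device's essential performance as structural support. The stated objective (Section 7) is also confined to the device's intended population, which Table 6 alone does not secure.

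**Working it through.** The plan derives no figure on this point, so the check sets the sections side by side.

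1. **Lower limit.** Table 2: above 45 kg. Table 6 and synopsis: above 45 kg. They agree.
2. **General upper limit.** Table 2: below 136 kg. Table 6 and synopsis: below 136 kg. They agree.
3. **Upper limit for high impact use.** Table 2: 110 kg. Table 6, synopsis, and Sections 8.2, 8.4 and 13.3: not mentioned.
4. **Impact level at screening.** Table 7 names a pain scale and the socket fit score for the telephone screen. No impact item is visible there or in Table 6.

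Applying both rules to each kind of subject:

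- Below 110 kg (and above 45 kg), any impact level: inside Table 6 and inside Table 2.
- Between 110 and 136 kg, no high impact use: inside both.
- Between 110 and 136 kg, high impact use: meets the weight criterion in Table 6, but outside Table 2.
- 136 kg or more: outside both.

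Only the third group is treated differently by the two tables.

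Width of the band: 136 − 110 = 26 kg. Width of the admitted range: 136 − 45 = 91 kg. Ratio: 26 / 91 = 0.286, about 29%. This describes the weight scale only. The documents give no weight distribution and no share of high-impact users, so the expected number among up to 13 subjects cannot be computed.

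Whether the third group can arise in practice depends on home use. The scheduled tasks are level walking, ramps, stairs, uneven terrain, TUG and 2MWT; no running is scheduled. The relevant exposure is the 4 weeks at home on a device that offers running. That running counts as high impact use is an assumption here, because the visible text does not define the term.

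**The case against.** The strongest reply is that nothing conflicts. The eligibility range equals the device's general range, and the 110 kg figure is a condition on a kind of use. A 120 kg subject who does not put the device to high impact use satisfies both tables. This stands. A reader might infer that Table 6 contradicts the device limit; the documents show an omitted condition and no clash of numbers.

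A reader might also infer that the plan has no impact restriction at all. That cannot be shown. Table 2 itself states the limit, the objective refers to the intended population, and Section 13.4 provides training by a qualified professional and product literature. The instructions for use and the training protocol are not in the visible text, and the annex is blacked out, so their content cannot be counted as absent. The claim has to stay with the eligibility criteria and the visible home-use text. Training and literature also come after the decision to enrol, so they do not do the work of a criterion.

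Section 13.2 lists as a foreseeable misuse "Use of product by user exceeding the maximum user weight". It is tempting to say that Table 6 admits exactly this misuse. As written it does not: a user in the band is below the general maximum, and only the further, undefined condition of high impact use could change that.

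Table 2 appears to treat activity level and impact level as separate items, so aiming at moderate to high active users does not show that subjects are high-impact users. Home use is not without contact either: Section 8.4 plans a call at 2 weeks and Section 14.2 refers to weekly contact. The rule in Section 14.2 that a serious device-related event ends the trial applies to every subject and adds no weight specific to this group.

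**Conclusion.** The point holds in limited form. The 110 kg figure for high impact use appears in Table 2 but is carried neither into the eligibility criteria nor into the visible home-use text. Followed as written, those sections allow a high-impact user of 110 to 136 kg to be enrolled and sent home although outside the Table 2 population.

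The conclusion assumes that Table 6 is the operative list and that no unseen document applies the limit at screening or release. A reader might take the 29% as a share of subjects; the documents do not support that, and the number affected could be zero. The matter is one of safety and consistency. It does not touch the endpoints, the sample size or the analysis, and it counts as a cheap improvement.

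**What to change.** Reconcile the synopsis, Table 6 and Sections 8.2, 8.4 and 13.3 with Table 2, so that either eligibility or the conditions of home use reflect both weight figures by impact level. State what counts as high impact use. Record each candidate's intended impact level at screening, next to body weight. If the instructions for use or training material already state the limit, an explicit cross-reference from Table 6 and the home-use text could carry part of this. The sponsor must decide which limit applies to whom; this review takes no view on that.

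The cost is one line of text and one screening field. Some heavier high-impact users may be excluded or restricted, which matters a little because recruitment is capped at 13 and Section 8.3 requires at least 10 to finish.
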